9.2.5 Other anti-tumor treatments

For subjects starting other anti-tumor treatments, unless suspected to be related to the study drugs, adverse events except death will be reported until the start of the new anti-tumor treatment. Deaths that occur within the SAE reporting period after study treatment is completed should be reported regardless of whether the subject has received other treatments.

9.2.6 SAE reporting

SAEs should be collected from signing the ICF to the end of safety follow-up period. In the event of an SAE, whether it is the first report or a follow-up report, the investigator must complete the "Serious Adverse Event Report Form" immediately, with a signature and date, and notify the sponsor within 24 h of knowing of the event. Relevant authorities must be informed of such SAE in a timely manner according to regulatory requirements.

Email the SAE reports to: [contact]

SAEs that occur after the safety follow-up period will generally not be reported unless suspected to be treatment-related. Symptoms, severity, causality with the study drugs, time of occurrence, duration of treatment, measures taken, follow-up time and methods, and outcomes of SAEs shall be documented. If an SAE is potentially related to the study conditions (e.g., discontinuation of previous therapy, or comorbidities during the study procedure) rather than the study treatment as deemed by the investigator, this relationship shall be detailed in the narrative section of the SAE report form. If the severity of an ongoing SAE or its relationship to the study drug changes, a follow-up report should be submitted immediately. If an error is found in a previously reported SAE, such SAE may be revised, revoked, or downgraded in follow-up reports and reported in accordance with the SAE reporting procedure.

9.2.7 Follow-up of AEs/SAEs

All the AEs/SAEs should be followed up until they resolve, recover to baseline levels or Grade ≤ 1 , steady state, or reasonably are explained (e.g., lost to follow-up, death).

During each visit, the investigator should ask about the situation of AEs/SAEs that occur after the last visit and provide follow-up information in a timely manner based on the sponsor's query request. Principles of collection and follow-up of AEs/SAEs after the last dose at the end of treatment are shown in the table below.

Principles of AE/SAE collection and follow-up

Classification	Collection/Documentation Requirements	Follow-Up Requirements
Unrelated AEs	Until the end of safety follow-up period or start of a new anti-tumor treatment (whichever comes first)	Until the end of safety follow-up period
Treatment-related AEs	Until the end of safety follow-up period	Until resolved, remission, or recovered to baseline levels or Grade ≤ 1 , steady state, or reasonably explained (e.g., lost to follow-up, death).
Unrelated SAEs (including SIEs)	Until the end of safety follow-up period or start of a new anti-tumor treatment (whichever comes first)	Until the end of safety follow-up period
Treatment-related SAEs (including SIEs)	No time limit	Until resolved, remission, or recovered to baseline levels or Grade ≤ 1 , steady state, or reasonably explained (e.g., lost to follow-up, death).

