16. Pulmonary function test: Maximum vital capacity, the forced expiratory flow at 25-75% of forced vital capacity (FEF25-75), the peak expiratory flow rate (PEF), the maximum expiratory volume per second, diffusing capacity of the lungs for carbon monoxide (DLCO) and oxygen saturation, which will be performed during the screening period and based on clinical indicators as determined by the investigator thereafter. Arterial blood gas test: optional. This test includes partial arterial pressure of oxygen (PaO₂), partial arterial pressure of carbon dioxide (PaCO₂), arterial oxygen saturation (SaO₂), and pH, and can be performed during the screening period. Pulmonary function test and arterial blood gas test indicators will be based on the actual conditions at each site.
17. Immunogenicity blood samples will be collected once within 0.5 h before SHR-1210 infusion on D1 of cycle 1, cycle 2, and the third cycle of every three cycles thereafter (cycles 5, 8, 11, etc.), once at the end of the treatment, and once per month at safety follow-ups after withdrawal for 3 times (if applicable). In case of national holidays, the blood collection time may be adjusted as appropriate. If the subject develops SHR-1210 infusion-related reactions, blood samples should be collected as close as possible to the onset of the event, to the end of the event, and about 30 days after the end of the event, for immunogenicity comparison and analysis. Immunogenicity blood samples should be collected following the study protocol. However, if deemed necessary by the investigator, unscheduled immunogenicity blood samples may be collected. Tests will be performed at the central laboratory. Four (4) mL of blood will be collected each time for immunogenicity.
18. The safety assessment for AEs and laboratory tests will be performed according to NCI CTCAE v4.03. All AEs/SAEs will be recorded in the CRF from the time of signing the ICF to the end of safety follow-up or the start of new anti-tumor therapy (whichever occurs first). The definition, recording, causality assessment, severity assessment, reporting time limit, handling, and follow-up of AE and SAE should refer to the description in Section 9 of the protocol.

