7.2 Main Study Procedures

7.2.1 Screening period (visit 1)

Refer to [Table 11](#) for procedures of visits during the screening period.

Table 11. Procedures of visits during the screening period

Period	Screening Period			Note
Day	-28 to -1	-7 to -1	-3 to -1	
Baseline				
ICF	X			Subjects who do not meet the relevant criteria of this study (screening failure) may be rescreened. See Section 7.1.1 of the protocol for rescreening procedures

Period	Screening Period			Note
	Day	-28 to -1	-7 to -1	
Inclusion/Exclusion Criteria	X			
Demographics/Medical History/Medication History	X			The medications include treatment for initial diagnosis, including chemotherapy, radiotherapy, and surgical treatment. The time of the last anti-tumor treatment must be recorded.
Vital Signs	X			Vital signs include body temperature, pulse, respiratory rate, and blood pressure. See Section 8.2.4 of the protocol for detailed requirements
Weight/Height	X			
Physical Examination	X			See Section 8.2.2 of the protocol
ECOG PS	X			
Laboratory tests				
12-Lead ECG	X			Refer to Section 8.2.3 of the protocol for details
Hematology/Clinical Chemistry/Urinalysis/Routine Stool		X		See Section 8.2.1 of the protocol
Coagulation Function		X		
Pregnancy Test			X	Serum pregnancy test
Thyroid Function	X			See Section 8.2.7 of the protocol
Myocardial Zymogram		X		See Section 8.2.7 of the protocol
Pituitary Adrenal Axis Test	X			Applicable to hospitals where conditions permit
HIV, HBV, and HCV	X			See Section 8.2.7 of the protocol
Echocardiography	X			See Section 8.2.7 of the protocol
Pulmonary function test and arterial blood gases	X			See Section 8.2.7 of the protocol
AE Assessment	X			All AEs from the time of signing the ICF to the end of safety follow-up or the start of new anti-tumor therapy (whichever occurs first) and all SAEs from signing of ICF to the end of safety follow-up will be recorded in the CRF
Concomitant Medications	X			Drugs related to the treatment of AEs other than solvents within 28 days before the first dose of the study drug until 30 days after and 30 to 60 days after the end of the treatment should be documented
Response Evaluation				

Period	Screening Period			Note
	Day	-28 to -1	-7 to -1	
Imaging Assessment	X			See Section 8.1 of the protocol
Exploration of Biomarkers				
Archived or Fresh Tumor Tissue Sample	X			5-10 unstained tissue slices with thickness of 4-6 μ m
Peripheral Blood	X			Collect 16 mL of peripheral blood for tumor biomarker detection

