9.1.1 Definition of AE

AE refers to any untoward medical condition in a clinical study subject who receives a pharmaceutical product, and the condition does not necessarily have a causality with the treatment. All AEs from signing of the informed consent form to the end of the safety follow-up period (90 days after the last dose) or the start of other anti-tumor treatments will be collected in this study. AEs can include any unfavorable and unintended symptoms, signs, abnormal laboratory findings, or diseases, including the following:

- 1) Worsening of pre-existing (prior to entering the clinical trial) medical conditions/diseases (including worsening symptoms, signs, or laboratory abnormalities);
- 2) Any new AE: Any new adverse medical conditions (including symptoms, signs, and newly diagnosed diseases);
- 3) Clinically significant abnormal laboratory findings.

All AEs should be documented in detail by the study personnel, including: the name of the AE and description of all relevant symptoms, onset time, severity, causality assessment, duration, measures taken, as well as final results and outcomes.

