5.5.1 Adverse events

Adverse events (AEs) will be analyzed based on the treatment-emergent adverse events (TEAEs):

- 1) All AEs that occur from the first study dose to 90 days after the last dose;
- 2) An AE that starts before the first study dose but worsens after administration.

Treatment-related AEs are defined as TEAEs with a causality of definitely related, possibly related, or indeterminable. If the relationship between an AE and the study drug is missing, the AE will be considered as a treatment-related AE.

All AEs will be coded with MedDRA 21.0. and graded by NCI-CTCAE v4.03. For the same SOC and/or PT, multiple cases of the same events that occur in one subject will be counted only once. For the same AE reported in one subject multiple times but varying in CTCAE grade, the AE of the greatest grade will be enumerated.

The incidence of AEs will be sorted from high to low based on their corresponding SOC in the SHR-1210 200 mg, IV, Q2W + apatinib 375 mg (or apatinib 250 mg), PO, QD group. The incidence of AEs in each SOC will be sorted from high to low based on their PT. If the incidences of \geq 2 PTs are equal, the AEs will be sorted alphabetically. If there is no AE under a SOC or PT, then analysis is not conducted.

The number of TEAE cases as well as the number of subjects based on the SS will be summarized in a table by dose group. The summary table should at least include the number of subjects with at least one TEAE/SAE/, TEAEs leading to treatment discontinuation, TEAEs leading to dose interruption or dose reduction, SAEs, SAEs leading to death, TEAEs of special interest, immune-related TEAEs (irAEs), and CTCAE grading. For all categories included in the summary table, CTCAE Grade ≥ 3 TEAEs and treatment-related AEs with an incidence of $\geq 5\%$ will be summarized by SOC and PT, respectively. Laboratory abnormalities with an incidence of $\geq 10\%$ will be summarized. TEAEs leading to treatment discontinuation, TEAEs leading to dose interruption or dose reduction, and all treatment-related AEs will be analyzed respectively for SHR-1210 and apatinib. An immune-related AE is determined in the case of an indeterminable immune-related AE.

In particular, the incidences and outcomes of AEs assessed per the CTCAE 4.03 below are separately analyzed:

- Hematologic toxicity
 - Grade 4, or
 - Grade ≥ 3 thrombocytopenia with hemorrhage, or
 - Grade ≥ 4 neutropenia with pyrexia and infection

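### The protocol gives conflicting rules for collecting adverse events after new anti-tumour therapy starts, and the SAP's TEAE window has no cut at that point

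*Protocol*

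**What the plan says.** Six places in the protocol say how long events are collected once a subject starts another anti-tumour treatment.

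- **Table 1, note 18** puts AEs and SAEs under one rule: "All AEs/SAEs will be recorded in the CRF from the time of signing the ICF" and then "to the end of safety follow-up or the start of new anti-tumor therapy (whichever occurs first". Causality plays no part. The note refers the reader to Section 9 for recording, reporting limits and follow-up.
- **Tables 11–14**, AE Assessment row, stop AEs at new therapy but not SAEs: "all SAEs from signing of ICF to the end of safety follow-up will be recorded in the CRF".
- **9.1.1** collects all AEs "to the end of the safety follow-up period (90 days after the last dose) or the start of other anti-tumor treatments", with no exception for related events.
- **9.2.5**, the section on subjects who start other treatment, stops reporting at that point except for suspected-related events and for deaths.
- **9.2.6** states "SAEs should be collected from signing the ICF to the end of safety follow-up period". It does not mention new therapy and does not split by causality. Later events are reported only if suspected to be related.
- **9.2.7**, table, collects unrelated AEs and unrelated SAEs "Until the end of safety follow-up period or start of a new anti-tumor treatment (whichever comes first". It collects related AEs to the end of safety follow-up and related SAEs without limit.

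SAP 5.5.1 defines TEAEs as "All AEs that occur from the first study dose to 90 days after the last dose", plus pre-existing AEs that worsen after dosing. It does not mention new anti-tumour therapy.

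**The concern.** AE incidence is a primary endpoint (Protocol 3.2.1, SAP 4.1), and any Grade 5 AE is one of its named components. Protocol 9.2.3 makes death from progression a reportable SAE. If sites may reasonably follow different instructions after new therapy starts, the same event is in the database at one site and absent at another. Because the SAP window stays open, whatever was recorded is then counted as treatment-emergent, including events that belong to the next line of treatment. The setting makes this plausible: Protocol 2.3.1 cites median PFS of 1.4 to 2.8 months and median OS of 5.7 to 7.7 months for nivolumab with or without ipilimumab in SCLC.

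**Working it through.** No sample size or error rate enters this point, so the check is a comparison of the rules. Take an event that occurs after new anti-tumour therapy starts and within 90 days of the last dose. For each rule, ask whether the event is collected (for the SAP, whether it is counted). SAEs are read as falling under 9.1.1, since they are AEs.

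| Rule | Unrelated non-serious AE | Related non-serious AE | Unrelated SAE, not death | Unrelated death | Related SAE |
|---|---|---|---|---|---|
| Table 1 note 18 | No | No | No | No | No |
| Tables 11–14 | No | No | Yes | Yes | Yes |
| 9.1.1 | No | No | No | No | No |
| 9.2.5 | No | Yes | No | Yes | Yes |
| 9.2.6 | not covered | not covered | Yes | Yes | Yes |
| 9.2.7 table | No | Yes | No | No | Yes |
| SAP 5.5.1 (counted) | Yes | Yes | Yes | Yes | Yes |

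Reading down the columns:

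1. **Unrelated non-serious AEs.** Every protocol rule that covers them stops at new therapy. The protocol is consistent here, but the SAP window still includes them, so one is counted only if a site recorded it anyway.
2. **Related non-serious AEs.** Note 18, Tables 11–14 and 9.1.1 stop; 9.2.5 and 9.2.7 continue.
3. **Unrelated SAEs other than death.** Note 18, 9.1.1, 9.2.5 and 9.2.7 stop; Tables 11–14 and 9.2.6 continue. Sections 9.2.6 and 9.2.7 are adjacent and give opposite instructions.
4. **Unrelated deaths.** Tables 11–14, 9.2.5 and 9.2.6 include them; note 18, 9.1.1 and the unrelated-SAE row of 9.2.7 do not.
5. **Related SAEs.** Note 18 and 9.1.1 stop; the other four continue.

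Reading across, the SAP row equals no protocol row that covers all classes. It agrees with Tables 11–14 and 9.2.6 on SAEs, and with 9.2.7 on related events up to day 90. After day 90 the position reverses: 9.2.7 still collects related SAEs, but they fall outside the TEAE window.

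Two other inconsistencies affect the same rules. Protocol 7.2.4 places safety follow-up at 90 ± 7 days in the text, but the header of Table 14 gives 28 ± 7 days, so the end of the period must itself be reconciled. The split in 9.2.7 also turns on relatedness. Protocol 9.1.3 counts events rated unlikely related as adverse drug reactions, whereas SAP 5.5.1 leaves them out of treatment-related AEs, so it is unclear which row of the 9.2.7 table applies to them.

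Without new anti-tumour therapy, every rule runs to the end of safety follow-up and this conflict does not arise.

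**The case against.** The best defence is that the documents rank these rules. Note 18 defers to Section 9. Within Section 9, 9.2.5 is written for exactly this situation and largely agrees with 9.2.7. On that view 9.1.1 and 9.2.6 are general statements that the specific sections override. Part of this stands: 9.2.5 and 9.2.7 do offer a basis for a single rule. It does not remove the conflict. Sections 9.1.1 and 9.2.6 are themselves in Section 9 and carry no such exception, Tables 11–14 side with 9.2.6 on SAEs, and 9.2.5 and 9.2.7 differ on unrelated deaths.

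A second objection is that a TEAE definition is an analysis window and not a collection rule. That is correct. A reader might infer that the SAP treats all 90 days as fully observed, but 5.5.1 does not say so and uses no person-time. The narrower point remains: an incidence over a window that is not collected uniformly depends on how sites read the protocol.

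A third is that few counts may change. SAP 5.5.1 counts a subject once per SOC or PT at the worst grade, so a late event matters only if it brings a new term, a higher grade or entry into a named category. This limits the effect. It gives no protection for Grade 5 events, where a death after new therapy can be the subject's only entry.

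**Conclusion.** The point holds in limited form. Once new anti-tumour therapy starts, the protocol has no single capture rule for related AEs, unrelated SAEs (including unrelated deaths) or related SAEs. The SAP leaves the TEAE window open across that period, so part of a primary endpoint depends on site interpretation and may include toxicity of the next treatment.

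Two stronger readings are not supported. One is that the SAP's 90 days has no basis in the protocol: 9.1.1 gives the same 90 days, and the window agrees with some of the rules for some classes, as shown above. The other is a numerical estimate drawn from the short PFS figures. Those come from other regimens and measure time to progression, not time from last dose to next therapy. Protocol 6.1.2 also allows treatment beyond progression. The documents give no rate of new therapy or of AEs within 90 days, so neither the size nor the net direction of the effect can be computed. The finding rests only on reading the current rules together. It does not threaten the trial's validity, but it should be settled before database lock.

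**What to change.** **Protocol.** State one rule, and repeat it unchanged in Table 1 note 18, Tables 11–14, 9.1.1, 9.2.5, 9.2.6 and 9.2.7. Sections 9.2.5 and 9.2.7 give a largely common basis: stop unrelated events at new therapy and continue related ones. Unrelated deaths still need aligning between those two sections. Reconcile the timing in 7.2.4 with the Table 14 header, and say how events rated unlikely related are classified.

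**SAP 5.5.1.** End the TEAE window at the earlier of 90 days after last dose or start of new anti-tumour therapy. Keep treatment-related events and deaths after new therapy, but only up to 90 days after last dose, so that the exception has a stated end. List related SAEs after day 90 separately. Show deaths after new therapy, including deaths from progression, separately from other Grade 5 TEAEs. Say what counts as new anti-tumour therapy for this cut, because SAP 5.4.2.2 leaves out radiotherapy for PFS while the definition in SAP 4.1 does not.

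**Cost.** Wording changes in both documents, and slightly fewer events counted as TEAEs. No new data item is needed: the start date of new therapy is already collected, and SAP 5.1.6.6 has an imputation rule for it. The SAP cut makes the count of unrelated events other than deaths uniform even where sites have followed different rules. It cannot recover related events or deaths that a site has already left unrecorded.

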9.3 Pregnancy

During the study, if a female subject becomes pregnant, she must immediately discontinue the study drug treatment. The investigator must report the event to the sponsor within 24 h of being notified and fill out the "Pregnancy Report/Follow-Up Form for Hengrui Clinical Studies".

During the study, if the partner of a male subject becomes pregnant, the subject can continue in the study. The investigator must report the event to the sponsor within 24 h of being notified and fill out the "Pregnancy Report/Follow-up Form for Hengrui Clinical Studies".

The investigator should follow up the outcome of the pregnancy until 1 month after delivery, and report the outcome to the sponsor.

Pregnancy outcomes such as stillbirth, spontaneous abortion, and fetal malformation are considered SAEs and need to be reported according to the time requirements for SAEs.

If the subject also experiences an SAE during the pregnancy, the "NMPA Serious Adverse Event Report Form" should also be filled out and reported according to the SAE reporting procedure.

9.4 Adverse Events of Special Interest

For adverse event of special interest (AESIs) specified in the study protocol, the investigator must complete the "Report of Adverse Event of Special Interest for Hengrui Clinical Studies" and report to the sponsor within 24 h of knowing of the event. If the AE of special interest is also an SAE, the "NMPA Serious Adverse Event Report Form" should also be completed and submitted to the relevant authorities according to SAE reporting procedure.

- Grade ≥ 3 infusion reaction
- Grade ≥ 3 other immune-related AEs

10 DATA ANALYSIS/STATISTICAL METHODS

10.1 Sample Size

In this study, based on historical study data and study results of drugs of the same class and combined with clinical needs, a single-stage assessment method will be adopted to explore the efficacy of SHR-1210 combined with apatinib on ORR in ED-SCLC after failure of the first-line standard therapy.

Assume that in this study, the expected ORR in each treatment group of SHR-1210 + apatinib combination therapy is $\geq 30\%$ (alternative hypothesis), and that there is no need to continue the study if the ORR is $\leq 15\%$ (null hypothesis), at the significance level of 0.1 and a power of 80%, 40 subjects should be enrolled. If ≥ 9 (22.5%) of the 40 subjects have response, it can be considered that the ORR in this treatment group is 15% and the study drug is worthy of continued development.

With a dropout rate of 10% taken into account, each treatment group needs to enroll about 45 subjects. A total of 57 subjects are required in Stages I and II.

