10.3 Statistical Hypotheses

This study does not involve any statistical hypotheses and inference.

A single-stage assessment method will be adopted to explore the efficacy of SHR-1210 combined with apatinib on ORR in ED-SCLC after failure of the first-line standard therapy. The potential need for further development is indicated when the predefined number of responses (objective response) of a treatment group is reached (see Section 10.1 for details).

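### The go rule of at least 9 responses in 40 has an exact type I error of 13.5%, above the stated 0.10; at 40 subjects only at least 10 meets both the stated level and 80% power

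*Protocol*

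**What the plan says.** Protocol 10.1 calls the design single-stage: "a single-stage assessment method will be adopted to explore the efficacy". The null ORR is 15% or less and the alternative is 30% or more. The operating characteristics are given as "at the significance level of 0.1 and a power of 80%, 40 subjects should be enrolled". The decision rule is nine or more responses: "22.5%) of the 40 subjects have response, it can be considered that the ORR in this treatment group is 15" per cent, after which the drug is considered worth developing further. The synopsis (Determination of Sample Size) and SAP 2.3 give the same rule with the same numbers. None of the three places names the test or says whether the 0.1 is one-sided or two-sided.

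Protocol 10.3 and SAP 3 say that the study involves no hypotheses or inference. Both then continue: "The potential need for further development is indicated when the predefined number of responses (objective response) of a treatment group is reached", referring back to the sample size section for the number.

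**The concern.** The cut-off, the sample size, the significance level and the power are stated together as one design, so they should agree with each other. A cut-off of 9 in 40 sits only three responses above the six expected under the null (40 × 0.15 = 6), which looks too close for an upper-tail error of 0.10.

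This count is the only numerical efficacy criterion in the plan. If it is too lenient, a regimen with an ORR at the uninteresting level is carried forward more often than the documents say. A result of exactly 9 of 40 would also be reported as meeting a 0.1 level that it does not meet.

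The closing clause adds a second problem. It says that reaching the cut-off shows an ORR of 15%, the null value, so the go statement literally asserts the no-go hypothesis.

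**Working it through.** **Inputs (Protocol 10.1; same in the synopsis and SAP 2.3).** Null p0 = 0.15; alternative p1 = 0.30; significance level 0.10; power 0.80; n = 40; go at X ≥ 9. Since 9/40 = 0.225, the printed 22.5% confirms that nine is the intended count.

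**Assumption.** The level is read as one-sided, because the rule acts only on high counts. This is also the reading kindest to the plan.

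**Formula.** For cut-off r, type I error = P(X ≥ r | n, p0) = 1 − P(X ≤ r − 1 | n, p0), and power = P(X ≥ r | n, p1), with X binomial.

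**The plan's rule, r = 9.**
- Type I error = 1 − P(X ≤ 8 | 40, 0.15) = 1 − 0.8646 = 0.1354
- Power = 1 − P(X ≤ 8 | 40, 0.30) = 1 − 0.1110 = 0.8890

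Neither 0.10 nor 80% is reproduced.

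**Neighbouring cut-offs at n = 40.**

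| Go if at least | Type I error (15%) | Power (30%) |
|---|---|---|
| 8 | 0.2441 | 0.9447 |
| 9 (plan) | 0.1354 | 0.8890 |
| 10 | 0.0672 | 0.8041 |
| 11 | 0.0299 | 0.6913 |

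Only 10 keeps the error within 0.10 and the power at 80% or more. Its power of 80.4% also matches the stated 80%.

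**Could nine belong to another n?** A cut-off of 9 meets both targets only at n = 37 (0.0924 and 0.8237). At n = 36 the power is 0.7963; at n = 38 the error is 0.1057.

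**Could another method give nine at n = 40?**
- *Uncorrected one-sided z-test.* The critical count is 40 × 0.15 + 1.2816 × √(40 × 0.15 × 0.85) = 6 + 1.2816 × 2.2583 = 8.89, so at least 9 (nominal p = 0.092). The matching sample size formula, ((1.2816√0.1275 + 0.8416√0.21)/0.15)² = 31.6, gives n = 32, and the approximate power at 40 is 85.8%. It explains the nine but not the 40 or the 80%.
- *With continuity correction.* The critical count is 9.39, so at least 10.
- *Mid-p for 9 of 40.* 0.0672 + ½ × (0.1354 − 0.0672) = 0.1013, still above 0.10.
- *Two-sided 0.10 (0.05 in the upper tail).* No cut-off at n = 40 reaches 80% power; the smallest exact design is at least 12 of 48 (0.0478 and 0.8186).

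**Check with Clopper-Pearson, the plan's interval method for ORR.** The one-sided 90% lower limit is 14.1% at 9/40, which does not exclude 15%, and 16.2% at 10/40, which does.

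**Effect between the hypotheses.** At a true ORR of 20%, P(X ≥ 9) = 0.407 and P(X ≥ 10) = 0.268.

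**The case against.** The best defence has four parts.

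1. *The test is not named.* An uncorrected z-test gives nine at n = 40 with a nominal p below 0.10, so the cut-off may come from that approximation and not from a slip of one. It stands that the origin cannot be settled from the documents: ≥ written for > is a plausible inference, not a fact. The defence does not rescue the rule, because that method gives n = 32 and the true error of the rule remains 13.5%.

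2. *The study is exploratory.* Inference is disclaimed, reaching the count only signals a possible need for further development, and safety must also be acceptable. The primary ORR report is an estimate with a two-sided 95% interval, which the cut-off does not change; at 9/40 its lower limit is 10.8%, visibly below 15%. All true, but the plan quotes a significance level and a power for this rule and makes it the efficacy criterion.

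3. *The excess is modest.* Against the stated 10% it is 3.5 percentage points, and power rises to 88.9%. That may be an acceptable trade for a phase II screen, but only if it is declared.

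4. *Changing nine to ten does not settle everything.* The FAS of the selected group could hold up to 45 subjects (6 from Stage I plus 39 from Stage II), and no cut-off is given for a denominator other than 40. If all 45 had a true ORR of 15%, at least 9 would have an error of 22.6% and at least 10 would have 12.7%. This is a separate gap. It does not weaken the point about the rule as stated for 40.

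**Conclusion.** The concern holds. As written, the go rule has an exact one-sided type I error of 13.5% and a power of 88.9%, not 0.10 and 80%. At 40 subjects, at least 10 responses is the only cut-off that meets both targets, with 6.7% and 80.4%. Compared with that rule, the printed one passes a regimen with a 15% ORR about twice as often (0.1354/0.0672 = 2.0).

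The result assumes exact binomial tails, a one-sided level and exactly 40 subjects analysed. A two-sided reading makes the breach larger. Two limits on the wording apply: at least 10 keeps the error within the 0.10 cap and does not attain 0.10; and the uniqueness applies to n = 40, since at least 9 of 37 also meets both targets.

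The statement that the ORR is 15% when the cut-off is reached is wrong whichever number is kept. Because this is the only efficacy decision rule and it is repeated in three places, it must be corrected.

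**What to change.** In the synopsis, Protocol 10.1 and SAP 2.3:

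- Change the rule to at least 10 (25%) of 40 subjects. State that the level is one-sided and exact, with type I error 6.7% and power 80.4%.
- If the sponsor prefers to keep nine, state the level as 13.5% and the power as 88.9%.
- In either case, say that reaching the cut-off indicates an ORR that exceeds 15%.
- These figures hold only for 40 analysed subjects, so say which 40 the rule applies to, or give the cut-off for the denominator actually analysed.

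The change should be made before responses are counted, and in any case before database lock, when Protocol 10.2 requires the SAP to be final. It costs document wording only, with no extra patients or procedures. The price is a go threshold one response stricter, or a less favourable stated significance level.
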